## 8.1. Adverse Events

At each visit, the Investigator will question the subject about adverse events using an open-ended question. If a potential adverse event is reported by the subject or identified during examination, directed questioning and examination will be performed when appropriate. At this time, the following will be performed:

1. Obtain a complete history of the event in question as well as conduct an examination of the subject and determine if the reported event qualifies as an Adverse Event. If the event is

determined to be an Adverse Event, an Adverse Event (AE) case report form and Event Follow-up (EF) Visit case report form must be completed. One AE case report form should be used to track the history of an individual AE throughout the period of the study.

- 2. Collect an updated medical and surgical history along with recording of concomitant medications or treatments.
- 3. Take photographs of the subject with attention to the area in question.
- 4. Render treatment for the event, if any, as determined by the medical judgment of the investigator.

Photographs will be taken to document any AEs if possible.

For the duration of the study, medical assistance will be provided to the subject for study-related problems at no expense, if in the opinion of the Investigator, the reaction was caused by the study device. Should a subject choose to seek their own medical treatment, no reimbursement will be offered.

When an AE persists at the end of the study, the Investigator will ensure a follow-up of the subject until the Investigator believes that the event is satisfactorily resolved.

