## 5.4.1 Randomization Groups

# 6. STUDY DESIGN

## 6.1. Outline of Procedures

Schedule of Events									
	Screening	Surgery	V	/ound Th	erapy Vis	its	Fo	llow-Up Vi	sits
	Visit 1	Visit 2	Visit 3	Visit 4*	Visit 5*	Visit 6	Visit 7	Visit 8	Visit 9
Procedures	Pre-Op	Surgery	2 Weeks	4 Weeks	6 Weeks	8 Weeks	3 Month s	6 Months	12 Months
ICF/Qualification/	x								
Enrollment	^								
Randomization	Х								
Standard/3D	v		v	v	v	v	v	v	Y
Photographs	^		^	^	^	^	^	^	~
Apply FMTB		Х	Х	Х	Х				
Skin Lab	~			v		v	v	v	v
Measurements	^			^		^	^	^	Λ
Skin Biopsies		Х		Х		Х	Х		Х
Colorimetry	Х		Х	Х	Х	Х	Х	Х	Х
POSAS						Х	Х	Х	Х
Blinded									v
Evaluations									A

\* Visit can be offered as in-person or telehealth visit

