## 6.4.1 Post-Surgical Procedures

- Subjects will be provided standardized instructions to encourage wound care for a total of 8 weeks.
- Supporting products (dressings etc.) will be provided to ensure compliance and an adequate supply to change dressing before next visits.
- 6.5. Wound Therapy Visits: Visits 3-6 (Weeks 2,4,6 and 8)
  - 1. A clinician will record any changes to the subjects' concomitant medications and will ask subjects if they have experienced any changes in their health since the previous visit. If an adverse event (AE) is reported, then the Investigator will be informed and an AE form will be completed.
  - 2. A clinician will clean and assess wounds. FMTB will be reapplied every two-weeks. If the visit

is being performed virtually, via telehealth, than the patient will be observed while cleaning his/her wound as well as during the reapplication of the FMTBs.

- 3. If in person, photographs will be taken of the wounds as described in section 7.1
- 4. If in person, skin lab measurements will be taken at visits 4 and 6 (weeks 4 and 8) as described in section 7.2.
- 5. If in person, biopsy samples will be obtained at visits 4 and 6 (weeks 4 and 8) as described in section 7.3
- 6. Supporting products will be provided to subject to ensure compliance. If patients opt to have telehealth visits for visits 4 and 6, FMTBs will be provided, as well as alcohol swabs for cleaning the skin. Patients will also be properly trained on how to apply the FMTBs themselves at prior visits if they plan to opt for telehealth visits.

These visits will take about 45 minutes

- 6.6. Follow-Up Visits: Visit 7-9 (Months 3, 6 and 12)
  - 1. A clinician will record concomitant medications and will ask subjects if they have experienced any changes in their health since the previous visit. If an adverse event (AE) is reported, then the Investigator will be informed and an AE form will be completed.
  - 2. Photographs will be taken of the wounds as described in section 7.1
  - 3. Skin lab measurements will be taken during each visit as described in section 7.2
  - 4. Biopsy samples will be obtained as described in section 7.3
  - 5. Patient and Observer Scar Assessment Scale will be completed by both the subject and clinician as described in section 7.4.

These visits will take about 45 minutes

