## 7.3. Biopsies

Four 0.33mm biopsies, two from each breast scar, will be obtained during multiple visits to assess histological evaluation and gene expression assessment. A subgroup of 10 patients will be selected to participate in the biopsy group. A local numbing agent, 0.5% Lidocaine with epinephrine, will be used to anesthetize the area being biopsied. The biopsy site will be cleaned and marked in the patients file, to keep consistency at all visits.

- Histological assessments will include epidermal and dermal ultrastructure, and immunofluorescence staining of collagen 1, collagen 3, elastin and fibroblast markers associated with fibrosis (smooth muscle actin and Dlk1).
- Gene expression assessment will include collagen and other major extracellular matrix (ECM) molecules and related to scar development.

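### No adverse-event contact is scheduled after the month-12 scar biopsies, and the no-cost care clause in 8.1 names only the device

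*Combined protocol and SAP*

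**What the plan says.** - **Who and what.** Section 7.3 states "A subgroup of 10 patients will be selected to participate in the biopsy group". In that group, "Four 0.33mm biopsies, two from each breast scar, will be obtained during multiple visits", under a local anaesthetic, for histology and gene expression.
- **When.** In the schedule in section 6.1, the row "Skin Biopsies" is marked at Visits 2, 4, 6, 7 and 9. Section 6.4 takes the Visit 2 samples from excised tissue, so scar sampling starts at Visit 4. Visit 9 (month 12) is the last column.
- **Follow-up visits.** In section 6.6, item 1 reads "A clinician will record concomitant medications and will ask subjects if they have experienced any changes in their health since the previous visit". Item 4 reads "Biopsy samples will be obtained as described in section 7.3".
- **Adverse events.** Section 8.1 has the Investigator ask an open question about adverse events at each visit. For the period after the study it says "When an AE persists at the end of the study, the Investigator will ensure a follow-up of the subject".
- **Care.** Section 8.1 offers medical assistance at no expense, during the study, for problems related to the study, on the condition "if in the opinion of the Investigator, the reaction was caused by the study device". Treatment that the subject seeks elsewhere is not reimbursed.
- **Risks.** Section 8 lists adhesive allergy, wound infection, irritation and blistering, and hypertrophic or keloidal scar. It has no entry for biopsy or local anaesthetic.

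**The concern.** The scar biopsies are an invasive procedure done purely for research, yet the safety provisions are written around the device and the operation. Two gaps follow.

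The first is in ascertainment. Active questioning is tied to visits, and the question looks back to the previous visit, so the effects of a biopsy are picked up at the next one. Visit 9 has no next one. The end-of-study rule follows an event that already exists at that point; it does not reach one that begins a few days later.

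The second is in cover. The care sentence opens broadly and then narrows to a single cause, the device. A volunteer with an infected biopsy site has a study-related problem that the device did not cause.

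At stake are the completeness of the biopsy safety record and the protection of the patients who agreed to the extra procedure. No efficacy endpoint, sample size or randomisation step is affected.

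**Working it through.** The plan states no figure on this point, so the check is a reading of the passages plus a count.

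**1. Is each scar-biopsy round followed by a scheduled adverse-event question?** (schedule in 6.1; sections 6.5, 6.6 and 8.1)

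| Biopsy round | Next scheduled adverse-event question |
|---|---|
| Visit 4 (week 4) | Visit 5 (week 6) |
| Visit 6 (week 8) | Visit 7 (month 3) |
| Visit 7 (month 3) | Visit 8 (month 6) |
| Visit 9 (month 12) | none |

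Three of the four rounds are followed up actively and the last is not.

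**2. How many cores does this concern?** Inputs: 10 patients and 4 cores per visit (7.3); scar biopsies at Visits 4, 6, 7 and 9 (6.1).

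- Per patient: 4 visits × 4 cores = 16.
- Subgroup: 16 × 10 = 160.
- Visit 9: 4 × 10 = 40.
- Share: 40 / 160 = 25%.

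**3. How firm is the 25%?** It assumes that all ten patients attend every biopsy visit in person. Section 6.5 takes the week-4 and week-8 biopsies only at in-person visits. The schedule marks Visits 4 and 5 as possible telehealth visits, while 6.5 also speaks of telehealth for Visits 4 and 6. Section 6.6 lists biopsies for Visits 7 to 9 without exception, although the schedule has none at Visit 8.

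| Reading | Total scar cores | Visit 9 share |
|---|---|---|
| Schedule as printed | 160 | 40/160 = 25% |
| Visit 8 biopsy added (6.6 read literally) | 200 | 40/200 = 20% |
| All Visit 4s remote | 120 | 40/120 = 33% |
| All Visit 4s and Visit 6s remote | 80 | 40/80 = 50% |

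Dropout is ignored here. With the 20% loss assumed in section 2.2, 8 of the 10 would reach Visit 9, giving 8 × 4 = 32 cores.

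**4. Do the self-report routes fill the gap?**

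- Section 8, Wound Infection: subjects should contact the investigator about oozing, strong pain, persistent swelling or signs of infection. It is written for the period after surgery.
- Section 8, Irritation & Blistering: subjects are asked to report these whenever they occur after surgery. There is no end date, but the text concerns the treatment area.
- Section 9.2: subjects are asked to make contact about events arising between visits, and an unscheduled visit is possible. The time after Visit 9 is not between visits.

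All three are passive, and none mentions biopsies.

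**5. Which biopsies does the care condition leave out?** The 8.1 condition turns on cause, not on date. It therefore excludes harm from any of the 16 scheduled scar cores per patient, not only the four at Visit 9. Because the clause also runs only for the duration of the study, harm appearing after Visit 9 may fall outside it on time as well.

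**The case against.** The strongest reply is that the plan is not silent. Patients are told to make contact about the very signs that an infected biopsy site would show. This stands: a reader might infer that delayed events have no way into the safety record, and the documents do not support that. What is missing is a scheduled, active question.

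A reader might also take the order of items in 6.6 to mean that the adverse-event question is always finished before the biopsy. The list is numbered but not stated to be a time sequence, and 8.1 does not fix when in a visit the question is asked. Immediate bleeding or an anaesthetic reaction could be seen in clinic by the staff present. This too stands and confines the gap to delayed events. Asking after the biopsy on the same day would still not detect those.

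On cover, the consent pages were removed from the text under review, and injury terms or biopsy risks may be set out there. One cannot conclude that patients would be refused care. What can be said is that the 8.1 wording is narrower than its own opening, and that it should match the consent form whatever that says.

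The point is also small: 10 of 42 patients, sub-millimetre cores, and no harm rate given. The 25% measures exposure, not events.

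Finally, a reader might infer that biopsy-site events could distort a safety comparison of the two closure methods. Sampling is symmetric, two cores per breast scar, and the documents plan no such comparison.

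**Conclusion.** The point holds for delayed harms and for the wording of 8.1. No adverse-event contact is scheduled after the Visit 9 biopsies, so for that round the record depends on patients reporting by routes that were not written for it. This concerns 40 of 160 scheduled scar cores (25%) under full in-person attendance, and roughly 20% to 50% under the other readings of the schedule and of sections 6.5 and 6.6. Separately, and for every scar-biopsy round, the care condition in 8.1 on its wording excludes harm from a research procedure.

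The conclusion rests on the protocol text alone, on Visit 9 being the last contact as the schedule shows, and on a subgroup of ten. It is a worthwhile low-cost improvement in participant protection and does not threaten the trial's efficacy results.

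**What to change.** 1. Add one telephone adverse-event check after the Visit 9 biopsies for the biopsy subgroup, and close their adverse-event window at that call.
2. In 8.1, extend the care condition to reactions caused by the study device or by a study procedure, and make it consistent with the injury terms in the consent form.
3. Add biopsy and local anaesthetic to the risks in section 8.
4. Reconcile 6.6 with the schedule on whether a biopsy is taken at Visit 8.

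Cost: up to ten calls, a wording amendment, a slightly later last-patient-out for the subgroup, and acceptance by the sponsor or site of cover for biopsy-related care. Endpoints, sample size and randomisation stay as they are.

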## 9. SUBJECT SAFETY AND DATA MONITORING

## 9.1. Research Standards/Good Clinical Practice

The conduct of this study will follow all applicable guidelines for the protection of human subjects for research as outlined in 21 CFR 50, in accordance with the accepted standards for Good Clinical Practice (GCP), International Conference on Harmonization (ICH), and the standard practices of UT Southwestern.

## 9.2. Data Monitoring

For this protocol, which involves the use of a non-significant risk device, the Investigator will monitor accrual, subject experience, attrition, patterns of adverse events and/or unexpected adverse events, any protocol deviations or violations any changes in the risk/benefit analysis.

Subjects will be asked about any adverse events throughout the study. Subjects will be asked to contact the Investigator if adverse events develop between visits. If necessary, an unscheduled visit will be arranged so that the Investigator can clinically evaluate and photograph these findings.

## 9.3. Procedures to Maintain Confidentiality

All study records and information will be identified by the subject number. All subject identifiers will be removed from all documents. The link between subject name and study ID number will be kept in separate password-protected files. Documents containing identifying information will be kept in locked files in the research staffs' locked office. All electronic study data will be password protected with access limited to members of the research team. No direct identifying information will be shared with any outside entities. Electronic data (electronic data entry - Case Report Forms) will be password protected.

Photographs of subject's surgical scars will be taken at enrollment and follow-up visits. These photographs will be identified by subject numbers and will not include any identifying marks [such as tattoos]. Subject confidentiality will be protected to the greatest extent possible.

This study will be performed in accordance with Health Insurance Portability and Accountability Act. These guidelines will be followed specifically with regard to the privacy and confidentiality of patient care and study records. Personnel associated with Investigator's office, the U.S. Food and Drug Administration (FDA) and the governing Institutional Review Board, have the right to review the data, including photographs, collected during this study.

Appendix I: POSAS Observer Scale

# **POSAS Observer scale**

The Patient and Observer Scar Assessment Scale v 2.0 / EN

Date of examination:		Name of patient:
Observer:		
Location:		Date of birth:
Research / study:		Identification number:
CRABAMETER	1 = normal skin wor	rst scar imaginable = 10
PARAMETER		
VASCOLARITY		
PIGMENTATIC	$\sim$ $\gamma\gamma\gamma\gamma\gamma\gamma\gamma$	
THICKNESS		
RELIEF	444444	
PLIABILITY	999999	
SURFACE ARE	• 000000	
OVERALL OPIN		0000
Explanation The observer scale of the POSAS of	onsists of six items (vascularity,	Explanatory notes on the items: • vasculative Presence of vessels in scar tissue assessed by the amount

- · VASCULARITY Presence of vessels in scar tissue assessed by the amount of redness, tested by the amount of blood return after blanching with a piece of Plexiglas to 10 ('worst scar imaginable'). The sum of the six items results in a total score of the POSAS observer
  - PIGMENTATION Brownish coloration of the scar by pigment (melanin); apply Plexiglas to the skin with moderate pressure to eliminate the effect of vascularity
  - THICKNESS Average distance between the subcutical-dermal border and the epidermal surface of the scar
  - RELIEF The extent to which surface irregularities are present (preferably compared with adjacent normal skin)
  - PLIABILITY Suppleness of the scar tested by wrinkling the scar between
  - the thumb and index finger SURFACE AREA Surface area of the scar in relation to the original wound area

#### Appendix 2: POSAS: Patient Scale

pigmentation, thickness, relief, pliability and surface area).

All items are scored on a scale ranging from 1 ('like normal skin')

scale. Categories boxes are added for each item. Furthermore, an overall

opinion is scored on a scale ranging from 1 to 10. All parameters should preferably be compared to normal skin on a

comparable anatomic location.

# **POSAS Patient scale**

The Patient and Observer Scar Assessment Scale v 2.0 / EN

Date of examination:	Name of patient:
Observer:	
Location:	Date of birth:
Research / study:	Identification number:
	1 = no, not at all yes, very much = 10
AS THE SCAR BEEN PAINFUL THE PAST FEW WEEKS?	 
HAS THE SCAR BEEN ITCHING THE PAST FEW WEEKS?	0000000000
	1 = no, as normal skin yes, very different = 10
	0000000000000
THE SCAR COLOR DIFFERENT FROM THE COLOR OF YOUR NORMAL SKIN AT I	
THE STIFFNESS OF THE SCAR DIFFERENT FROM YOUR NORMAL SKIN AT PRES	
THE THICKNESS OF THE SCAR DIFFERENT FROM YOUR NORMAL SKIN AT PRE	
5 THE SCAR MORE IRREGULAR THAN YOUR NORMAL SKIN AT PRESENT?	

Brijjit Protocol 18APR2025.pdf 17 of 17

Appendix 3: Handheld Pantone SkinTone Guide
